Appendix G. Non-Responder Imputation Incorporating Multiple Imputation

G.1 Sample SAS Code for Binary Variable

```
PROC MI DATA=REMI 2 OUT=REMI FULL NIMPUTE = 30 SEED = XXXXX
/*RANDOM SEED PRE DEFINED IN SAP*/
DECIMAL*/;
MINMAXITER = 1000;
CLASS TRT01PN STRATA1N STRATA2N STRATA3N BASE WK2 WK4 WK8 WK12
WK16 WK20 WK24 WK28 WK36 WK44 WK52; /*SPECIFIES THE
CLASSIFICATION VARIABLES IN THE VAR STATEMENT*/
VAR TRT01PN STRATA1N STRATA2N STRATA3N BASE WK2 WK4 WK8 WK12 WK16
WK20 WK24 WK28 WK36 WK44 WK52;
FCS LOGISTIC (BASE= TRT01PN STRATA1N STRATA2N STRATA3N);
FCS LOGISTIC (WK2= TRT01PN STRATA1N STRATA2N STRATA3N BASE);
FCS LOGISTIC (WK4= TRT01PN STRATA1N STRATA2N STRATA3N BASE WK2);
FCS LOGISTIC (WK8= TRT01PN STRATA1N STRATA2N STRATA3N BASE WK2
WK4);
FCS LOGISTIC (WK12= TRT01PN STRATA1N STRATA2N STRATA3N BASE WK2
WK4 WK8);
FCS LOGISTIC (WK16= TRT01PN STRATA1N STRATA2N STRATA3N BASE WK2
WK4 WK8 WK12);
FCS LOGISTIC (WK20= TRT01PN STRATA1N STRATA2N STRATA3N BASE WK2
WK4 WK8 WK12 WK16);
FCS LOGISTIC (WK24= TRT01PN STRATA1N STRATA2N STRATA3N BASE WK2
WK4 WK8 WK12 WK16 WK20);
FCS LOGISTIC (WK28= TRT01PN STRATA1N STRATA2N STRATA3N BASE WK2
WK4 WK8 WK12 WK16 WK20 WK24);
FCS LOGISTIC (WK36= TRT01PN STRATA1N STRATA2N STRATA3N BASE WK2
WK4 WK8 WK12 WK16 WK20 WK24 WK28);
FCS LOGISTIC (WK44= TRT01PN STRATA1N STRATA2N STRATA3N BASE WK2
WK4 WK8 WK12 WK16 WK20 WK24 WK28 WK36);
FCS LOGISTIC (WK52= TRT01PN STRATA1N STRATA2N STRATA3N BASE WK2
WK4 WK8 WK12 WK16 WK20 WK24 WK28 WK36 WK44);
```

[figure not shown]
RUN;

G.2 Sample SAS Code for Dichotomized Outcome Variable

```
/*NOTE: THIS APPROACH REQUIRES NO MISSING IN CATEGORICAL
COVARIATES AND REQUIRES AT LEAST ONE OBSERVATION IN BASELIBE OR
ONE OF THE POSTBASELINE VISIT*/
/*PRE AUGMENTATION CREATE DUMMY FOR CATEGORICAL VARIABLES*/
/**************/
DATA PGIC 2; SET PGIC;
/*THE MCMC STATMENT BELOW ASSUMES MULTI VARIATE NORMAL*/
/*IF TREATMENT OR ANY COVARIATES ARE CATEGORICAL WITH L>2
LEVELS*/
/*NEED TO CREATE L 1 DUMMY VARIABLES*/
/*HERE, TREATMENT (TRT01PN) HAS 3 LEVELS, SO WE NEED 2 DUMMY
VARIABLES*/
IF TRT01PN=1 THEN TRT1=1; ELSE TRT1=0;
IF TRT01PN=2 THEN TRT2=1; ELSE TRT2=0;
IF STRATA1N=1 THEN STRATA1N1=1; ELSE STRATA1N1=0;
IF STRATA2N=1 THEN STRATA2N1=1; ELSE STRATA2N1=0;
IF STRATA3N=1 THEN STRATA3N1=1; ELSE STRATA3N1=0;
/*THIS IS TO TRANSFER STRATIFICATION FACTORS INTO NUMERICAL FORM
FOR GETTING PGIC MONO STEP BELOW*/
RUN:
/*AUGMENTATION STEP TO HAVE 30 MONOTONE MISSING DATASETS*/
PROC MI DATA=PGIC 2 OUT=PGIC MONO NIMPUTE=30 SEED= XXXXX /*RANDOM
SEED PRE DEFINED IN SAP*/
ROUND=. . . . 0.1 0.1 0.1 0.1 /*VALUE ROUND TO 1ST DECIMAL*/
MIN=. . . . 1 1 1 1/*MINIMUM VALUE OF PGIC IS 1*/
MAX=. . . . . 7 7 7; /*MAXIMUM VALUE OF PGIC IS 7*/
MCMC IMPUTE=MONOTONE ;
/*NOTE: CATEGORICAL VARIABLES SUCH AS TRT1 TRT2 ARE DUMMY,
CREATED ABOVE*/
/*NOTE: ALL OTHER NON DUMMIED COVARIATES MUST BE CONTINUOUS*/
/*SUPPOSE STRATA2N (NUMERIC VARIABLE FOR STRATA) HAS ONLY 2
LEVELS, NO NEED TO CREATE DUMMY*/
VAR TRT1 TRT2 STRATA1N1 STRATA2N1 STRATA3N1 WK8 WK12 WK24 WK52;
/*CAUTION TO USE THE "BY" STATEMENT IN MCMC: */
/*MVN MODEL IS FITTED WITHIN EACH 'BY' GROUP, INSTEAD OF ACROSS
ALL GROUPS*/
RUN;
/*IMPUTATION STEP DETERMINE IMPUTATION DISTRIBUTION AND RANDOMLY
IMPUTE MISSING VALUE TO GENERATE 'COMPLETE' DATASETS*/
/***************/
PROC MI DATA= PGIC MONO OUT= PGIC FULL NIMPUTE=1 SEED=XXXXX
/*RANDOM SEED PRE DEFINED IN SAP*/
ROUND=. . . . . 0.1 0.1 0.1 0.1 /*VALUE ROUND TO 1ST DECIMAL*/
MIN=. . . . 1 1 1 1/*MINIMUM VALUE OF PGIC IS 1*/
```

```
MAX=. . . . . 7 7 7; /*MAXIMUM VALUE OF PGIC IS 7*/
MINMAXITER=1000;
CLASS TRT01PN STRATA1N STRATA2N STRATA3N;
VAR TRT01PN STRATA1N STRATA2N STRATA3N WK8 WK12 WK24 WK52;
MONOTONE REG (WK12 = TRT01PN STRATA1N STRATA2N STRATA3N WK8);
MONOTONE REG (WK24 = TRT01PN STRATA1N STRATA2N STRATA3N WK8
WK12);
MONOTONE REG (WK52 = TRT01PN STRATA1N STRATA2N STRATA3N WK8 WK12
WK24);
/* IMPUTED SEQUENTIALLY, FROM WK 12 TO 52, WITH COVARIATES
CONSTRUCTED FROM THE CORRESPONDING PRECEDING
VARIABLES*/
BY IMPUTATION; /*FOR EACH OF THE 30 MONOTONE MISSING DATASETS,
IMPUTE A 'COMPLETE' DATASET*/
RUN:
/*DETERMINE DICHOTOMOUS RESPONSE STATUS FOR PGIC*/
DATA ALL; SET PGIC FULL;
IF . <WK8<=2 THEN PGIC 8=1;</pre>
ELSE PGIC 8=0;
IF . <WK12<=2 THEN PGIC 12=1;</pre>
ELSE PGIC 12=0;
IF . <WK24<=2 THEN PGIC 24=1;</pre>
ELSE PGIC 24=0;
IF . \langle WK52 \langle =2 \rangle THEN PGIC 52=1;
ELSE PGIC 52=0;
RUN:
/*********************
*****
/* DATA HANDLING STEPS TO MERGE COVID 19 STATUS OMITTED
/* PLACE TO ADD DATA HANDLING AND MERGING STEPS
/**********************
*****
/*OVERRIDE MISSING VALUES NOT DUE TO COVID 19 WITH TRADITIONAL
NRI*/
DATA ALLF; SET ALL;
/*COVID19 XX='Y' IF MISSING AT WEEK XX IS DUE TO COVID 19; IF
NOT.
OVERRIDE WITH TRADITIONAL NRI*/
IF COVID19 8 NE 'Y' THEN PGIC 8=PGICNRI 8;
```

```
/*VARIABLE IBDQ NRI XX: TRADITIONAL NRI DATA AT WEEK XX, WHICH
COVERS
THE SPECIAL HANDLING SUCH AS THE BEFORE AND AFTER EXCEPTION*/
IF COVID19 12 NE 'Y' THEN PGIC 12=PGICNRI 12;
IF COVID19 24 NE 'Y' THEN PGIC 24=PGICNRI 24;
IF COVID19 52 NE 'Y' THEN PGIC 52=PGICNRI 52;
RUN:
PROC SORT DATA=ALLF; BY IMPUTATION SUBJID; RUN;
/***********
/*ANALYSIS MODEL*/
/************/
/*KEY CODE: ANALYZING EACH 'COMPLETE' DATASET*/
/***********
/*INDIVIDUAL LEVEL DATA > # OF RESPONDERS & # OF SUBJECTS, TO
BE READIN
TO PROC STDRATE*/
PROC FREQ DATA=ALLF;
BY IMPUTATION;
TABLES TRT01PN*STRATAN*PGIC 52/LIST NOCUM NOPRINT
OUT=COUNT TABLE;
/*WEEK 52 RESULTS AS AN EXAMPLE*/
DATA COUNT TABLE; SET COUNT TABLE;
DROP PERCENT;
RUN;
PROC TRANSPOSE DATA=COUNT TABLE OUT=FREQ TABLE PREFIX=RESP;
ID PGIC 52;
BY IMPUTATION TRT01PN STRATAN;
VAR COUNT;
RUN:
DATA FREQ TABLE1; SET FREQ TABLE;
CASE=RESP1;
SIZE=SUM(RESPO, RESP1);
KEEP IMPUTATION TRT01PN STRATAN CASE SIZE;
RUN:
/*RE ORDER TO SET 1 (PLACEBO) AS THE REFERENCE GROUP*/
DATA FREQ TABLE2; SET FREQ TABLE1;
IF TRT01PN=2 THEN TRT01PN=0;
RUN:
/*CALCULATE THE COMMON RISK DIFF FOR EACH COMPLETE DATASET*/
PROC STDRATE DATA=FREQ TABLE2
METHOD=MH STAT=RISK EFFECT=DIFF;
BY IMPUTATION;
POPULATION GROUP=TRT01PN EVENT=CASE TOTAL=SIZE;
```

Version 2.0 – 14 February 2024

```
STRATA STRATAN / ORDER=DATA STATS (CL=NONE) EFFECT;
ODS OUTPUT EFFECT=EFFECT;
RUN;
/*COMBINING RESULTS USING PROC MIANALYZE*/
/****************

PROC MIANALYZE DATA=EFFECT;
ODS OUTPUT PARAMETERESTIMATES=RISK;
MODELEFFECTS RiskDiff;
STDERR StdErr;
RUN;
```

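### The PGIC imputation code in SAP Appendix G.2 gives COVID-missing visits too low a response rate, because a bounded normal score rounded to 0.1 is dichotomised at 2

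*SAP*

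**What the plan says.** SAP Section 9.5 treats PGIC as a responder endpoint, with response meaning either of the two best named categories. Sections 3.3 and 9.5 list it among the additional endpoints, outside the multiplicity-controlled set in Section 3.2.

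Appendix G.2 sets out how missing PGIC is imputed:

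- **Model.** The augmentation step carries the comment "THE MCMC STATMENT BELOW ASSUMES MULTI VARIATE NORMAL". The imputation step is then a sequence of linear regressions by visit, for example "MONOTONE REG (WK12 = TRT01PN STRATA1N STRATA2N STRATA3N WK8".
- **Bounds.** Comments in the code state "MINIMUM VALUE OF PGIC IS 1" and "MAXIMUM VALUE OF PGIC IS 7".
- **Rounding.** Both PROC MI calls round to 0.1, with the comment "VALUE ROUND TO 1ST DECIMAL". The first reads "ROUND=. . . . 0.1 0.1 0.1 0.1 /*VALUE ROUND TO 1ST DECIMAL".
- **Response rule.** "IF . <WK8<=2 THEN PGIC 8=1", with the same rule at the other visits, for example "IF . <WK24<=2 THEN PGIC 24=1".
- **Where it is used.** The imputed response is kept only where the visit is missing because of COVID-19. Elsewhere it is overwritten with the traditional non-responder value. This agrees with Section 9.2.

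No step maps the imputed score back to a category before the response rule is applied. Appendix H gives PGIC its own seeds for both steps.

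**The concern.** A rule of 2 or below captures the whole of category 2 when scores are whole categories. On a score recorded to 0.1 it captures only raw values below 2.05. Values from 2.05 up to 2.5 lie nearest to category 2 but are scored as failures.

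There is a second cause. A PGIC distribution with a good response rate is skewed and piled up at 1 and 2. A normal curve with the same mean and SD puts appreciable mass below 1. The bound at 1 removes that mass and spreads it over the allowed range, which shifts imputed scores upward.

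Multiple imputation is used here so that a visit lost to COVID-19 logistics is not automatically a failure. An imputed response rate that is too low puts part of that forced non-response back.

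**Working it through.** The documents give no figure for this point, so there is none to reproduce. They also give no PGIC distribution, visit correlation or COVID-missing rate. Those below are assumptions, shown over a range.

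**Inputs from the SAP:** normal model, bounds 1 and 7, rounding to 0.1, response at 2 or below (Appendix G.2); response as the top two categories (Section 9.5); 30 imputations (Section 9.2).

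**Step 1: one imputed visit, ignoring covariates.** Take an assumed distribution over categories 1 to 7, with mean m and SD s. Treat the bounds as redraws, so that the imputed score is a normal truncated to 1–7. Then

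P(response) = [Φ((c − m)/s) − Φ((1 − m)/s)] / [Φ((7 − m)/s) − Φ((1 − m)/s)],

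with c = 2.05 as coded and c = 2.5 for whole-number rounding or a cut below 2.5.

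Worked case: 15, 35, 25, 15, 6, 3 and 1% in categories 1 to 7.

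- True response = 0.15 + 0.35 = 0.500; m = 2.75; s = √(9.27 − 2.75²) = 1.307.
- Φ at 1, 2.05, 2.5 and 7: 0.0902, 0.2961, 0.4241, 0.9994.
- As coded: (0.2961 − 0.0902)/(0.9994 − 0.0902) = 0.226.
- Cut at 2.5: (0.4241 − 0.0902)/0.9092 = 0.367.
- Total shortfall: 0.500 − 0.226 = 0.274. The 2.5 cut removes 0.367 − 0.226 = 0.141, about half, and leaves 0.133.

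The remaining 0.133 comes from the model. Without the bounds, the 2.5 cut would give 0.424. So 0.424 − 0.367 = 0.057 is due to truncation, and 0.500 − 0.424 = 0.076 to fitting a normal curve to a skewed score.

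The same formula for other assumed distributions:

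| Assumed response | m, s | As coded | Cut at 2.5 | Shortfall left after the 2.5 cut |
|---|---|---|---|---|
| 80% | 1.97, 1.15 | 41.0% | 59.6% | 20.4 points |
| 65% | 2.28, 1.23 | 32.6% | 49.7% | 15.3 points |
| 60% | 2.47, 1.31 | 28.0% | 43.5% | 16.5 points |
| 50% | 2.75, 1.31 | 22.6% | 36.7% | 13.3 points |
| 30% | 3.23, 1.29 | 14.4% | 25.5% | 4.5 points |
| 15% | 4.00, 1.45 | 7.3% | 13.6% | 1.4 points |

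Other assumed shapes with 50–70% response gave about 22–35% as coded and 34–52% with the 2.5 cut. The direction reversed only for a distribution with no true responders (0.000 true, 0.010 as coded).

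**Step 2: conditional imputation and the effect on an arm.** A simulation used regression imputation with parameter draws and 30 imputations. It had 210 against 105 subjects with assumed response of 65% and 50%, and four visits with adjacent-visit correlation 0.5 or 0.8. Week 52 values were missing at random with the same probability in both arms, with 200 replicates per setting. The model used treatment and the three earlier visits; strata were left out.

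- Imputed subjects responded at 0.34–0.41 (65% arm) and 0.24–0.28 (50% arm) as coded, against 0.51–0.58 and 0.38–0.44 with whole-number rounding.
- At 2% missing, an arm's rate fell by 0.5–0.6 points (for example 0.646 against 0.652).
- At 10% missing, it fell by about 2–3 points (0.478 against 0.500; 0.619 against 0.649).
- The treatment difference moved by 0.3 points or less (largest: 0.146 against 0.149).

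**The case against.** The strongest reply is that this hardly matters, and most of that reply stands. PGIC is an additional endpoint, imputed values survive only at COVID-missing visits, and the same code runs in every arm, so the error largely cancels in the comparison. The appendix is also headed as sample code and keeps placeholder seeds and a comment naming a different questionnaire. Even so, it is the only specification of PGIC imputation, it is written for PGIC by name, and Appendix H fixes PGIC seeds. A programmer who follows it will reproduce the low rate.

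One can also say that the SAP never calls the scale an integer scale. That is true, but the 1–7 bounds and the named response categories leave no room for an observed 2.3.

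Two stronger readings are tempting and are not supported:

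- A reader might infer that observed and imputed subjects are held to different cut-points. They are not: G.2 uses one rule, 2 or below. What differs is granularity, since only imputed scores can fall between categories.
- A reader might infer that the rounding is the whole cause, so that rounding to whole numbers settles it. The table shows otherwise: at 50–65% response, 13–17 points of shortfall remain, and they come from the bounded normal model.

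**Conclusion.** The point holds as a minor one. As coded, COVID-missing PGIC visits are imputed with too low a response rate, for two reasons: decimal scores meet a whole-category rule, and a bounded normal is a poor model for a skewed seven-category score. With assumed response of 50–70%, roughly half of the responders among imputed visits are lost.

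The reported results would move little: about 0.5 to 3 points on an arm's PGIC rate at 2–10% missing, and 0.3 points or less on the treatment difference. The latter figure assumes equal missing rates in the arms. If 10% were imputed in one arm and 2% in the other, shifts of about 3.0 and 0.5 points would not cancel, and the difference would move by about 3.0 − 0.5 = 2.5 points. The documents give no reason to expect such an imbalance from COVID-19 logistics.

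It would be wrong to infer a threat to the trial's main conclusions. The primary endpoint and the multiplicity-controlled endpoints do not use this code. All sizes rest on assumed PGIC distributions, visit correlations and missing rates, and on reading the bounds as redraws.

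**What to change.** Preferred: derive the PGIC response at Weeks 8, 12, 24 and 52 from the observed categories, then impute that binary response by sequential logistic FCS, as G.1 already does. Drop the baseline term, since PGIC is not collected at Baseline. An ordinal model for the score is an equally good alternative. Either way, no cut-off is applied to a fractional score.

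Minimum: keep G.2 but round the final imputed score to whole numbers, or set the response at an imputed value below 2.5. State that this is partial. It removes about half of the shortfall in the unconditional check at 50–65% response, and rather more when visits are strongly correlated: at correlation 0.8 and 10% missing in the 65% arm, (0.571 − 0.398)/(0.648 − 0.398) = 69%.

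The cost is a short code edit in Appendix G and, for the preferred option, an update of the PGIC seed entry in Appendix H. No observed data, endpoint definition or testing order changes.

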Appendix H. Random Seeds

In case of non-convergence, the random seed will be updated by adding 10000 at each attempt in order to avoid the non-convergence issue that is caused by specific random seeds.

A. Random Seeds for NRI-MI for Binary Endpoints

Endpoint	Random Seed	
Remission related endpoints	21586*	
GCA-related health resource utilization	21587	

^{*} This is SAS numerical form of Feb 06, 2019, which is the first subject randomized in the study.

B. Random Seeds for NRI-MI for Dichotomized Endpoints

	Random Seed			
Endpoint	MCMC Procedure PROC MI			
PGIC	21588	21589		

C. Random Seeds for Tipping Point Analysis for Continuous Endpoints

Endpoint	Random Seed for x% Shift towards the Worse Direction for UPA group and y% Shift towards the Better Direction for PBO group
SF-36 PCS	(1+(x/200+y/10)%)*30000
FACIT-Fatigue	(1+(x/200+y/10)%)*50000
TSQM patient global satisfaction subscore	(1+(x/200+y/10)%)*70000

D. Random Seeds for Tipping Point Analysis for Binary Endpoint

Endpoint	Random Seed for x% Shift towards the Worse Direction for UPA group and y% Shift towards the Better Direction for PBO group in z replicate
Disease flare	(1+(x/200+y/10)%)*90000+z
